3.5.2 Safety Analysis Population

The APaT population will be used for the analysis of safety data in this study. The APaT population consists of all randomized participants who received at least 1 dose of study intervention. Participants will be included in the intervention group corresponding to the study intervention they actually received for the analysis of safety data using the APaT population. For most participants, this will be the intervention group to which they are randomized. Participants who take incorrect study intervention for the entire intervention period will be included in the intervention group corresponding to the study intervention

actually received. Participants who take incorrect study intervention during only a part of the treatment period and took at least 1 dose of active study intervention will be included in the active treatment group.

At least 1 laboratory or vital sign measurement obtained subsequent to at least 1 dose of study intervention is required for inclusion in the analysis of each specific parameter. To assess change from baseline, a baseline measurement is also required.

3.6 STATISTICAL METHODS

Statistical testing and inference for efficacy and safety analyses are described in Sections 3.6.1 – Statistical Methods for Efficacy Analyses and 3.6.2 – Statistical Methods for Safety Analyses, respectively. Unless otherwise stated, all statistical tests will be conducted at an overall significant level of 0.05 (2-sided).

3.6.1 Statistical Methods for Efficacy Analyses

The analysis of efficacy endpoints will be based on the FAS population. Unless otherwise specified, analyses will include all follow-up efficacy data collected for those participants who discontinued treatment.

Primary Efficacy Analysis

The LCQ is collected at baseline and after administration of the study intervention at Weeks 6 and 12. The primary efficacy endpoint of this study is the LCQ change from baseline in total score. The primary analysis approach will be conducted utilizing the longitudinal ANCOVA model. In this model, the response vector consists of the LCQ change from baseline in total score at each post-Baseline visit. The model will include factors for intervention group, visit, interaction of treatment by visit, gender, and the baseline LCQ score. The model will use all available LCQ change from baseline in total score at Weeks 6 and 12. Contrasts will be constructed to compare the Gefapixant intervention group to the Placebo group at Week 6 and Week 12. The least squares mean change from baseline with the associated standard errors will be displayed for each intervention group. Overall estimated treatment differences (Gefapixant – Placebo) along with corresponding p-values and 95% CIs will also be presented, with the exception of the primary efficacy endpoint, in which the CI width will be adjusted for an IA.

Secondary Efficacy Analysis

The secondary efficacy endpoint will be analyzed using a similar longitudinal ANCOVA model as used for the primary efficacy analysis. The model will include terms for intervention group, visit, interaction of treatment by visit, gender, and baseline score.

[Table 1](#) summarizes the analysis strategy of the primary and secondary efficacy endpoints.

Table 1 Analysis Strategy for Key Efficacy Endpoints

Endpoint/Variable (at Week 12)	Statistical Method	Missing Data Approach
Primary		
Change from baseline in LCQ total score	Longitudinal ANCOVA	Model-based ^a
Secondary		
Change from baseline in Cough Severity VAS score	Longitudinal ANCOVA	Model-based ^a
ANCOVA = analysis of covariance; LCQ = Leicester Cough Questionnaire; VAS = Visual Analogue Scale		
^a Includes data collected after early intervention discontinuation.		

Exploratory Efficacy Analysis

- **CSD Total Score**

Change from baseline of the weekly average total daily CSD score and three subscales will be analyzed using a similar longitudinal ANCOVA model as used for the primary efficacy analysis in the original scale.

- **PGIC and PGIM Questionnaire**

The self-report measure PGIC reflects a participant's belief about the efficacy of treatment. PGIC is a 7-point scale depicting a participant's rating of overall improvement. Participants rate their change as “much better”, “better”, “a little better”, “the same”, “a little worse”, “worse”, or “much worse”. PGIM is a subsequent question that asks participants to indicate whether the level of change they report on the PGIC is a meaningful change, with yes/no response.

The numbers and proportions of participants with each response to the PGIC questionnaire will be provided at Week 12 by treatment group. Participants with improvements (“much better”, “better”, or “a little better” on the PGIC scale) and participants with a response of yes in the PGIM questionnaire to indicate important change for the improvement will be summarized. Proportion of participants with improvements will be analyzed by the stratified (region and gender) Miettinen and Nurminen (M&N) method.

- **WPAI Questionnaire**

The WPAI questionnaire consists of 6 questions and yields four types of scores over the past 7 days as follows: (1) absenteeism (work time missed); (2) presenteeism (impairment at work / reduced on-the-job effectiveness); (3) work productivity loss (overall work impairment/absenteeism plus presenteeism); and (4) activity impairment. The WPAI outcomes are expressed as impairment percentages, with higher numbers indicating greater impairment and less productivity, ie, worse outcomes. The 4 scores of the questionnaire are

expressed as impairment percentages: the percent work time missed due to problem ($Q2/(Q2+Q4)$), the percent impairment while working due to problem ($Q5/10$), the percent activity impairment due to problem ($Q6/10$), and overall percent work impairment score due to problem $Q2/(Q2+Q4)+[(1-(Q2/(Q2+Q4))x(Q5/10)]$.

Change from baseline in each of the 4 scores will be analyzed using an ANCOVA model. The response vector consists of the change from baseline in WPAI at Week 12. The model will include factors for intervention group, visit, gender, and the baseline WPAI score.

Handling of Missing Data and Sensitivity Analyses

A participant will be considered for inclusion in the assessment of an efficacy endpoint if the CSD and Cough Severity VAS are completed on at least 4 days during the 7-day period prior to a post-Baseline visit (other ePROs are completed at the clinic visit only). All efficacy analyses will be conducted based on the observed data only. No imputation is planned for the missing diaries or missing questionnaire items. The pattern of missing is assumed to be missing at random (MAR). The missing pattern will be inspected to determine if the MAR assumption is met. Sensitivity analyses will be implemented to explore the impact of departures from the assumption made in missing diaries.

The longitudinal ANCOVA model (aka. LDA method) assumes that data are missing at random. In this study, it is expected that missing at random and missing completely at random (MAR/MCAR) mechanisms will underlie most of the missingness, and the proportion of data missing not at random (MNAR), driven solely by unobserved values of the study endpoints, will be small.

In addition to the analysis approach specified in the above mentioned primary efficacy endpoint analysis section, the following sensitivity analyses will be used to assess the robustness of the primary analysis approach.

Tipping-point Multiple-imputation Analysis

The Variant 3 of the tipping point as described in paper [Ratitch et al. 2013] will be used. In that approach, missing data are first imputed for all visits under the MAR assumption, and then the worsening/shift is applied. This is repeated with increasing the delta-shift (worsening) until the result is no longer statistically significant. Specifically, for a given constant, c , the tipping point analysis is conducted in a fashion similar to that used in standard multiple imputation, whereby m ($=100$) complete datasets are randomly generated using the original observed dataset. These m complete datasets are subsequently analyzed using the primary model, and the results of those analyses are then combined. The construction and analysis of these m ($=100$) datasets requires four primary steps:

- 1) Using a Markov Chain Monte Carlo method, make the observed dataset monotone-missing. This will be accomplished for each treatment group using “proc mi” within SAS 9.3 or higher by utilizing the options “mcmc chain=multiple impute=monotone;”, in conjunction with all of the covariates (excluding treatment)

included in the primary analysis model. The random seed will be set equal to 72644243. This step will generate m monotone-missing datasets.

- 2) Applying parametric regression to the monotone-missing datasets, impute all the missing values. This will be accomplished for each treatment group using “proc mi” within SAS 9.3 or higher utilizing the option “monotone reg”, in conjunction with all of the covariates (excluding treatment) included in the primary analysis model. The random seed will be set equal to 72644243. This step will generate m complete datasets.
- 3) To implement the tipping-point aspect of the procedure, subtract a constant c from each of the imputed values of the active arms (to the detriment of active).
- 4) Analyze each of the post-imputation complete datasets using the primary model, obtaining point estimates for the mean of interest (e.g. change-from-baseline treatment difference at 12 weeks) and the associated variance.

Using “proc mianalyze” within SAS 9.3 or higher, the $m=100$ means and variances from the m analyses will be combined to obtain the final test statistic and p-value (Rubin, 1987). The final test statistic $\bar{Q} / (T^{-1/2})$ is approximately distributed as t_v , where \bar{Q} is the sample mean of the m treatment difference estimates, $T = \bar{U} + (m+1) (B/m)$, \bar{U} is the sample mean of the m variance estimates, and B is the sample variance of the m treatment difference estimates. The degrees of freedom, v , will be computed as follows [Barnard and Rubin, 1999]: $v = [(v_1)^{-1} + (v_2)^{-1}]^{-1}$, where $v_1 = (m-1) [1 + (\bar{U}/(1+m^{-1}) B)]^2$ and $v_2 = (1-\gamma) v_0 (v_0 + 1) / (v_0 + 3)$, with $\gamma = (1+m^{-1}) B / T$ and where v_0 represents the complete-data degrees of freedom .

This procedure will be repeated (using the same m imputed datasets) until the smallest c is found such that the significant result turns non-significant (i.e., $p > 0.05$). This tipping point value c provides a measure of robustness of the primary result. A relatively large value of c implies better robustness of the primary analysis against the impact of missing data in the study. It is noted that when $c=0$ the tipping point analysis described above corresponds to an analysis conducted under the assumption that the missing data are MAR. For values of c larger than 0, the tipping point analyses do not assume that the missing values follow a MAR mechanism. In fact, the analysis is based on a special MNAR mechanism in which all missing data across the arms are assumed to have a worse response by a constant amount of c than the values would have had under MAR.

Jump-to-reference (J2R) Multiple-imputation Analysis

J2R imputation falls under the category of pattern mixture models known as reference-based imputation (RBI). The RBI approach uses different imputation models for missing data in different treatment groups. In J2R, missing data in the control group are imputed under the MAR assumption, while missing data in the treatment groups are imputed under a MNAR assumption using the control group profile for time points after withdrawal.

The following steps will be used to implement the J2R multiple-imputation analysis.

- 1) A parameter-estimation model is fitted using PROC MCMC. All the covariates included in the primary analysis will be used for the parameter-estimation model. For the MCMC procedure, an initial random seed=72644243 will be used. N=500 sets of pseudo-independent samples of the model parameters will be drawn from the joint posterior distribution.
- 2) The imputation model is built, where, for each pattern of withdrawal, a predicted value model is created using the parameters estimated in Step 1. The random seed for the imputations is 72644243. For subjects in the control (reference) group, the predicted means are calculated under MAR assumption; for subjects in the other treatment arms, the predicted means are calculated under MNAR using the jump-to-reference approach, that is, the mean profile is based on the same treatment arm before withdrawal and ‘jumps’ to the mean profile based on the reference arm after withdrawal. A complete dataset will be generated using the imputation model for each set of the N=500 parameters obtained in Step 1.
- 3) For each of the imputed complete datasets, an ANCOVA model will be used for the change from baseline values at last time point. The model will include the same covariates as in the primary analysis model. The treatment difference across the 500 datasets will then be combined using PROC MIANALYZE, i.e., using Rubin’s rule for multiple imputation (Rubin, 1987) to provide the final results.

The J2R sensitivity analysis was implemented using macros developed by the DIA (Drug Information Association) Missing Data Working Group, which were available on page of www.missingdata.org.uk.

To get correct variance for the jump-to-reference imputation method, a pattern mixture model approximation will also be used. Based on the definition, the jump-to-reference imputation will have 0 mean treatment difference between treatment and control for those who dropped out in the treatment arm. Therefore, the overall mean treatment difference for jump-to-reference becomes

$$\theta^{J2R} = (\pi_t \mu_t^d + (1 - \pi_t) \mu_t^p) - \mu_t^p = \pi_t (\mu_t^d - \mu_t^p)$$

where π_t is the proportion of completers in the drug group, t is the last time point, and μ_t^d and μ_t^p are the mean effects for drug and control, respectively. It can be estimated from the primary analysis model as $\hat{\theta}^{J2R} = \hat{\pi}_t (\hat{\mu}_t^d - \hat{\mu}_t^p)$. The variance can be approximated by,

$$\text{var}(\hat{\theta}^{J2R}) = \hat{\pi}_t^2 \text{var}(\hat{\mu}_t^d - \hat{\mu}_t^p) + (\hat{\mu}_t^d - \hat{\mu}_t^p)^2 \hat{\pi}_t (1 - \hat{\pi}_t) / n$$

where n is sample size in the drug treatment arm. The first term can be estimated from the primary analysis model.

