6.3.2 Stratification

Intervention allocation/randomization will be stratified according to the following factors:

1. Gender (Male, Female)
2. Geographical region (North America, Europe, Asia-Pacific, Other). Details of the regions will be provided in the separate supplemental document for randomization.

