9 STATISTICAL ANALYSIS PLAN

This section outlines the statistical analysis strategy and procedures for the study. If, after the study has begun, but prior to any unblinding, changes are made to primary and/or key secondary hypotheses, or the statistical methods related to those hypotheses, then the protocol will be amended (consistent with ICH Guidance E9). Changes to exploratory or other non-confirmatory analyses made after the protocol has been finalized, but prior to unblinding, will be documented in a sSAP and referenced in the CSR for the study. Post-hoc exploratory analyses will be clearly identified in the CSR.

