9.2 Responsibility for Analyses/In-house Blinding

The statistical analysis of the data obtained from this study will be the responsibility of the designee of the Sponsor.

This study will be conducted as a double-blind study under in-house blinding procedures. The official, final database will not be unblinded until medical/scientific review has been performed, protocol deviations have been identified, and data have been declared final and complete. The investigator site personnel and the participants will be blinded to intervention assignment until the entire study completion.

The Clinical Biostatistics department will generate the randomized allocation schedule(s) for study intervention assignment. Treatment assignment will be implemented in an IRT system by a study vendor according to the adaptive allocation scheme provided in Section 6.3.1.

Blinding issues related to the planned IA are described in Section 9.7.

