9.6.1 Statistical Methods for Efficacy Analyses

The analysis of efficacy endpoints will be based on the FAS population. Unless otherwise specified, all efficacy data from participants who have taken at least 1 dose of study intervention will be included in efficacy analyses.

Primary Efficacy Analysis

The LCQ is collected at baseline and after administration of the study intervention at Weeks 6 and 12. The primary efficacy endpoint of this study is the LCQ change from baseline in total score. The primary analysis approach will be conducted utilizing the longitudinal ANCOVA model. In this model, the response vector consists of the LCQ change from baseline in total score at each post-Baseline visit. The model will include factors for intervention group, visit, interaction of treatment by visit, gender, and the baseline LCQ score. The model will use all available LCQ change from baseline in total score at Weeks 6 and 12. Contrasts will be constructed to compare the Gefapixant intervention group to the Placebo group at Week 6 and Week 12. The least squares mean change from baseline with the associated standard errors will be displayed for each intervention group. Overall estimated treatment differences (Gefapixant – Placebo) along with corresponding p-values and 95% CIs will also be presented, with the exception of the primary efficacy endpoint, in which the CI width will be adjusted for an IA (Section 9.6). Further details of the model specification, assumptions, and SAS implementation codes will be provided in the sSAP.

Secondary Efficacy Analysis

The continuous secondary efficacy endpoints will be analyzed using a similar longitudinal ANCOVA model as used for the primary efficacy analysis. The model will include terms for intervention group, visit, interaction of treatment by visit, gender, and baseline score.

Table 4 summarizes the analysis strategy of the primary and secondary efficacy endpoints.

Table 4 Analysis Strategy for Primary and Secondary Efficacy Endpoints

Endpoint/Variable (at Week 12)	Statistical Method	Missing Data Approach
Primary		
Change from baseline in LCQ total score	Longitudinal ANCOVA	Model-based ^a
Secondary		
Change from baseline in Cough Severity VAS score	Longitudinal ANCOVA	Model-based ^a
ANCOVA=analysis of covariance; LCQ=Leicester Cough Questionnaire; VAS=Visual Analog Scale		
^a Includes data collected after early intervention discontinuation.		

The strategy for the IA is described in Section 9.7.

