If the unstructured covariance matrix fails to converge with the default algorithm, then the AR(1) structure can be used to provide initial values of the covariance parameters.

Example SAS Codes

```
proc mixed data=adeff;
  where avisitn > 0;
  class subjid trt01p avisitn sex;
  model chg = base trt01p avisitn sex trt01p*avisitn/ solution notest;
  repeated avisitn / subject = subjid type=un;
  lsmestimate trt01p*avisitn 'MK at Week 12' [1, 1 2];
  lsmestimate trt01p*avisitn ' Placebo at Week 12' [1, 2 2];
  lsmestimate trt01p*avisitn 'Treatment Differences at Week 12' [1, 1 2] [-1, 2 2];
run;
```

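### Region stratifies the randomisation but is missing, without explanation, from the LCQ, VAS, CSD and WPAI models; adding it costs almost nothing and helps if region is prognostic

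*Combined protocol and SAP*

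**What the plan says.** Protocol 6.3.2 names two stratification factors. One is gender; the other is "Geographical region (North America, Europe, Asia-Pacific, Other").

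The LCQ model in sSAP 3.6.1 uses only the first: "The model will include factors for intervention group, visit, interaction of treatment by visit, gender, and the baseline LCQ score". The same terms appear in protocol 9.1 and 9.6.1 and in sSAP 3.1 and 4.1. The example code has "class subjid trt01p avisitn sex" in its CLASS statement, and its MODEL statement has no region term either.

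The other continuous endpoints follow suit:

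- VAS (protocol 9.6.1, repeated in sSAP 3.6.1): "The model will include terms for intervention group, visit, interaction of treatment by visit, gender, and baseline score".
- WPAI (sSAP 3.6.1): "The model will include factors for intervention group, visit, gender, and the baseline WPAI score".
- CSD (sSAP 3.6.1): a model similar to the primary one, so region is omitted by reference.

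The exception is PGIC. In sSAP 3.6.1 the proportion improved "will be analyzed by the stratified (region and gender) Miettinen and Nurminen (M&N) method". Region is also an LCQ subgroup factor (protocol 9.10, sSAP 3.10). Neither document says why gender is kept in the models and region is not.

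**The concern.** Stratifying by a factor makes the arms similar on it. If the factor predicts outcome, this lowers the true sampling variance of the treatment difference. A model that omits the factor leaves the between-stratum variance in the residual, so it reports a standard error that is too large, a confidence interval that is too wide and a test that is somewhat conservative. If the arms are not balanced within region, the reported standard error is correct, but precision that adjustment could have gained is lost.

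In neither case is the estimate biased or type I error inflated. What is at stake is some power and interval width in the only confirmatory test, from a factor already recorded and randomised by. The plan also treats its own strata unevenly: an exploratory endpoint uses both and the primary endpoint uses one.

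**Working it through.** **Inputs.** From sSAP 3.9: difference 1.1, SD 3.5, one-sided alpha 0.024 at the final analysis, 352 evaluable participants (176 per arm) after 15% dropout. Assumed, because the documents give no figure: R², the share of residual variance that region explains after baseline and gender, from 0 to 10%.

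**The plan's own figures.**
- 352/0.85 = 414.1, matching 414 randomised; 0.001 + 0.024 = 0.025.
- SE = 3.5 × √(2/176) = 0.3731; z(0.024) = 1.977.
- Power = Φ(1.1/0.3731 − 1.977) = 83.4%, which meets the stated minimum of 80%.

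**Case (a): arms balanced within region.** The true SE is 0.3731 × √(1 − R²) under either model. Without region, the model still reports about 0.3731. Then:
- SE overstatement = 1/√(1 − R²) − 1
- Actual type I error = 1 − Φ(1.977/√(1 − R²))
- Power without region = Φ((1.1 − 1.977 × 0.3731)/true SE)
- Power with region = Φ(1.1/true SE − 1.977)
- CI half-width with region = 1.977 × true SE

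| R² | SE overstated | Type I error without region | Power without | Power with | Points forgone | Half-width with region |
|---|---|---|---|---|---|---|
| 0% | 0% | 0.0240 | 83.4% | 83.4% | 0 | 0.738 |
| 2% | 1.0% | 0.0229 | 83.7% | 84.2% | 0.5 | 0.730 |
| 5% | 2.6% | 0.0212 | 84.0% | 85.3% | 1.2 | 0.719 |
| 10% | 5.4% | 0.0186 | 84.7% | 87.1% | 2.4 | 0.700 |

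Without region the half-width stays at 0.738 throughout.

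**Case (b): arms not balanced within region.** The reported SE is right, type I error stays at 0.024 and power without region stays at 83.4%. The points forgone are 0, 0.7, 1.8 and 3.7, before the small variance cost given below.

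**Cost of adding region.** Three degrees of freedom out of about 350. At R² = 0 with balanced arms, noncentral-t power moves from 83.213% to 83.211%. With unbalanced arms the variance rises by about 3/348, so SE = 0.3731 × √(1 + 3/348) = 0.3747 and power is 83.1%, a loss of about 0.3 points.

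**Simulation checks of case (a)**, single-visit models with assumed region shares and blocked allocation within gender by region:
- R² = 10%, 15% random dropout, 8,000 runs: power 84.6% without region and 87.2% with it; mean estimate 1.105 under both models against a true 1.1.
- R² = 5%, 6,000 runs: mean reported SE 0.373 without region and 0.363 with it; the actual spread of the estimates was 0.363 under both.

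**The case against.** The best counter-argument is that nothing here is an error. The covariates are prespecified and consistent across protocol, sSAP and code, the estimate is unbiased and the power statement holds. The benefit depends on an assumed R²; at 2% with balanced arms it is half a point of power. That is fair, and it is why this is an efficiency recommendation and not a validity finding.

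Several narrower points also have substance:

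- **SD.** The 3.5 is the SD of change from baseline and may not be covariate-adjusted. If baseline and gender already explain 10, 20 or 30% of it (assumed), power without region is already about 87, 91 or 94% at region R² = 0, and the balanced-case loss at R² = 5% falls from 1.2 to about 1.0, 0.8 or 0.6 points. The gain shrinks but keeps its direction.
- **Precision.** With balanced arms, adding region corrects the reported SE, interval and test; it does not make the estimate itself less variable. A true precision gain arises only in case (b).
- **Balance.** Protocol 9.2 says treatment is assigned "according to the adaptive allocation scheme provided in Section 6.3.1", but 6.3.1 describes no such scheme. Balance within region is therefore an assumption. The advice is the same in both cases.
- **Amendment.** The amendment rule covers the primary and key secondary hypotheses and their methods. Only LCQ has a hypothesis, and the CSD and WPAI models stand only in the sSAP, so an sSAP entry is enough for those two. The LCQ change still needs an amendment.
- **WPAI.** Its work scores exist only for employed participants, so the power figures here do not carry over to it.

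The region subgroup analysis does not answer the concern, because it does not adjust the primary test.

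**Conclusion.** The concern holds as an efficiency point. A stratification factor is omitted from the primary model and from the VAS, CSD and WPAI models without explanation. On the sSAP 3.9 inputs, the LCQ cost ranges from 0 points of power (region not prognostic) to 2.4 points (R² = 10%, balanced arms) or about 3.7 points (R² = 10%, unbalanced arms, before the small variance cost). At R² of 5% or less it is under 2 points. With balanced arms the final test also runs below its nominal 0.024, down to 0.0186 at R² = 10%. These sizes rest on the assumed R², on 3.5 being the residual SD, and on a single-visit approximation to the two-visit model without a futility stop. Validity and the planned power are not in question.

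**What to change.** Add region (North America, Europe, Asia-Pacific, Other) as a fixed effect beside gender in the LCQ, VAS, CSD and WPAI models. The places to change are protocol 9.1 and 9.6.1 and sSAP 3.1, 3.6.1 and 4.1, including the CLASS and MODEL statements. The tipping-point and jump-to-reference imputations in sSAP 3.6.1 take the primary model's covariates, so carry region into them too. Set a pooling rule for sparse regions, notably Other, while still blinded.

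For LCQ this must be a protocol amendment before any unblinding. Protocol section 9 says that if changes are made to the primary hypothesis "or the statistical methods related to those hypotheses, then the protocol will be amended". Since an external statistician is unblinded for the interim analysis, the safe timing is before that analysis.

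The cost is the amendment with its regulatory and ethics review, matching sSAP text and code, and three degrees of freedom. No new data are needed. If region was left out on purpose, one sentence giving the reason would settle the matter.
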